6.3. Randomization and Blinding

6.3.1. Randomization

In the course of this study, subjects will be randomized twice:

- 1) After subjects complete the screening period and meet the inclusion criteria after D1 pre-dose assessment, they can be randomized to Group A (CBP-201 300 mg Q2W) or Group B (placebo Q2W) in a 2:1 ratio before D1 administration;
- 2) Subjects who are assessed to have met the response criteria before W16 administration will be randomized to Group C (CBP-201 300 mg Q2W) or Group D (CBP-201 300 mg Q4W) in a ratio of 1:1.

Subjects will be stratified and randomized according to their baseline disease severity (moderate [IGA=3] and severe [IGA=4]) to avoid bias and increase the likelihood of keeping

known and unknown subject attributes (e.g., demographics and other baseline characteristics) or other variables balanced between treatment groups and increase the validity of statistical comparisons between treatment groups.

The placebo control will be used to determine the frequency and magnitude of changes in clinical endpoints that may occur in the absence of active drug treatment, and to minimize the bias of subjects and investigators.

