8.2.2. Permitted Drugs/Treatments

a. AD recurrence and rescue therapy

AD is a chronic recurrent skin disease characterized by periodic aggravation or gradual deterioration of symptoms. If medically necessary (i.e. in order to control intolerable AD symptoms), the investigator can provide patients with rescue therapy for AD by using drugs or treatment regimens that were originally prohibited at their own discretion. According to the investigator's judgment, AD aggravation or deterioration of symptoms which requires drugs or treatments originally prohibited by the protocol for rescue therapy will be defined as "AD recurrence" event, and the onset and duration of these events will be recorded as AE according to the site of attack.

Note: The investigator should limit the first-step rescue therapy to topical drugs (TCS or TCI) as far as possible. Only patients who do not respond adequately after at least 7 days of topical medication can be upgraded to systemic medication or other treatments. If a subject receives systemic corticosteroid or non-steroid systemic immunosuppressive/immunomodulatory rescue therapy, the study drug administration will be stopped immediately.

b. Other drugs that are permitted may include:

- Emollients (as the background treatment of this study, at least 7 days before baseline, all subjects need to use mild emollients at least twice a day, and continue to use them throughout the study period. During the screening period or the study period, subjects cannot start using prescription emollients or emollients containing additives. However, if a subject has already started using these emollients before the screening visit, he/she can continue using them at a stable dose throughout the study period. If the subject is intolerable to the emollients provided uniformly by the sponsor during the screening period, he/she can change to the emollient of this kind used previously, but it must be used at a stable dose for at least 7 days before baseline and during the study period.);
- Basic skin care (cleansing and bathing);
- Oral antihistamines (maintain a stable dose within 7 days before baseline and during the study period);
- Drugs for the treatment of chronic diseases (e.g., hypertension, diabetes, etc.);
- Local or systemic anti-infective drugs (as required by the condition).

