12.3. Basis of Sample Size

The sample size of 255 cases (in a 2:1 ratio, 170 cases in the CBP-201 300 mg Q2W group, and 85 cases in the placebo group. Assuming that the dropout rate in the treatment group is 15%, then about 144 cases in the CBP-201 300 mg Q2W group and 72 cases in the placebo group will be able to complete the study) can provide a power of 90% to detect the therapeutic effect on the primary endpoint in the CBP-201 300 mg Q2W group and the placebo group. This power is calculated based on the following assumption: the proportion of subjects reaching the primary efficacy endpoint is 27% in the CBP-201 300 mg Q2W group and 9% in the placebo group, and the significance level for two-sided tests is 0.05.

Based on the results of another conducted phase II international multicenter clinical study of CBP-201 in patients with moderate-to-severe atopic dermatitis, the proportion of subjects reaching the primary efficacy endpoint was 28.1% in the CBP-201 300mg Q2W group and 10.7% in the placebo group, at a two-sided test significance level of 0.05, and if the results of this trial are similar to that of the WW001 trial, the above sample size would provide a power of more than 85% to detect the therapeutic effect on the primary endpoint between the CBP-201 300 mg Q2W group and the placebo group. Therefore, no adjustment is made to the sample size.

The primary analysis of this study will still be based on the 255 subjects enrolled in accordance with V2.1 and its earlier versions of the protocol. Subjects newly enrolled (approximately 81 cases) based on the protocol after V2.1 will not be included in the primary analysis, and only supplementary analysis will be performed.

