7.4.4. Other efficacy endpoint analysis

The categorical efficacy endpoint analysis in Stage 1 will be performed using the same method as the primary efficacy endpoint analysis.

The continuous efficacy endpoint analysis in Stage 1 will be performed using the same method as the secondary efficacy endpoint analysis.

According to the investigator's judgment, AD aggravation or deterioration of symptoms which requires drugs or treatments originally prohibited by the protocol for rescue therapy will be defined as "AD recurrence" event.

The number of AD recurrence, the number of subjects with AD recurrence, and the number of days of AD recurrence in Stage 1, from baseline to W8, from W9 to W16 will be analyzed. The total number of AD recurrence in each stage will be summarized. AD recurrence will be summarized by the number of recurrences, that is, 0, 1, 2 and ≥ 3 . The number and percentage of subjects will be calculated. Chi-squared test will be adopted to compare whether the differences between the two groups are statistically significant. The total number of subjects with AD recurrence in each stage will be summarized, and the number and percentage of subjects will be calculated. Chi-squared test will be performed to compare whether the differences between the two groups are statistically significant. The number of days of AD recurrence in each stage will be summarized by descriptive statistics.

7.4.5. Efficacy analysis in stage 2

During efficacy analysis in Stage 2, the percentage of subjects achieving efficacy endpoint and its confidence interval will be calculated for categorical efficacy endpoints. For continuous efficacy endpoints, ANCOVA model will be used to calculate the mean, the Least Square Mean, 95% confidence interval and SE of the change from baseline and percentage change from baseline of each efficacy endpoint. The model will include treatment group, severity of baseline disease (IGA 3 or 4), and baseline value of corresponding endpoint. Inferential statistics will not be performed during the Stage 2 analysis. The following two analyses will be performed.

Analysis method 1: Categorical efficacy endpoints after the occurrence of events will be regarded as no response for subjects who have the following conditions; continuous efficacy endpoints after the occurrence of events will be imputed using WOCF in Stage 2; other missing data except for the conditions above will be imputed using multiple imputation (MI).

- Group adjustment

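### The chi-squared test named for AD recurrence (SAP 7.4.4) omits the IGA stratum and ignores the ordering of 0, 1, 2 and ≥3 recurrences; most of the avoidable power loss comes from the ordering

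*SAP*

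**What the plan says.** SAP 7.4.4 opens with a general rule: "The categorical efficacy endpoint analysis in Stage 1 will be performed using the same method as the primary efficacy endpoint analysis". SAP 7.4.3 defines that method as a Cochran-Mantel-Haenszel test on differences in response rates, stratified by baseline disease severity (IGA 3 or 4). The stratum matches the design; Protocol 6.3.1 says: "Subjects will be stratified and randomized according to their baseline disease severity".

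Later in 7.4.4, AD recurrence in Stage 1 and its two sub-periods is tabulated as 0, 1, 2 and ≥3 recurrences, and the test is given as: "Chi-squared test will be adopted to compare whether the differences between the two groups are statistically significant". An almost identical sentence covers the number of subjects with any recurrence. Neither sentence names a stratum, a trend or a set of scores. SAP Version 1.0 names the same test in the same places.

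On data capture, Protocol 8.2.2 says of AD recurrence that "the onset and duration of these events will be recorded as AE according to the site of attack". SAP 7.4.4 gives no rule for turning those records into episodes or days.

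AD recurrence is listed among the other efficacy endpoints (SAP 4.1.3), outside the fixed testing sequence in SAP 7.4.

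**The concern.** There are two separate issues.

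- **Consistency.** A general rule pointing to a stratified test is followed by an endpoint-specific sentence with no stratum. The natural reading is that recurrence is an exception and gets an ordinary chi-squared test. Two programmers could reasonably differ.
- **Efficiency.** The four categories are ordered. An ordinary chi-squared test on a 2×4 table spreads its sensitivity over 3 degrees of freedom and gives the same answer if the columns are shuffled. A treatment that shifts subjects towards fewer recurrences is better detected by a 1-df test that uses the order.

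At stake is the chance of detecting a real reduction in flares that need rescue, on a supportive endpoint. Separately, if one flare at several sites produced several records, a subject could move up the count categories whichever test is used.

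**Working it through.** **Inputs from the documents.** Two-sided level: "the significance level for two-sided tests is 0.05" (Protocol 12.3). Allocation is 2:1, with 170 on CBP-201 and 85 on placebo, and the stratum is IGA 3 versus 4. No AD-recurrence rate is given. The nearest proxies are adverse-event rates from other studies: AD deterioration in 26.1% on CBP-201 and 37.5% on placebo (Protocol 4.4.2), and AD events in 15% on CBP-201 (Protocol 4.4.4).

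**The plan's own figure.** The only power statement is for the primary endpoint. The protocol says the sample "can provide a power of 90% to detect the therapeutic effect on the primary endpoint", at rates of "27% in the CBP-201 300 mg Q2W group and 9% in the placebo group". With pooled variance, r = 2 and p̄ = (0.09 + 2×0.27)/3 = 0.21:

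n(placebo) = [1.960·√(0.21·0.79·1.5) + 1.282·√(0.09·0.91 + 0.27·0.73/2)]² / 0.18² = (0.978 + 0.544)² / 0.0324 ≈ 71.5, so 72 placebo and 144 active.

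Allowing for 15% dropout, 72/0.85 = 84.7 and 144/0.85 = 169.4, giving 85 + 170 = 255. Power at 72/144 is 90.2%. At the earlier study's "28.1% in the CBP-201 300mg Q2W group and 10.7% in the placebo group" it is 85.9%, matching the stated figure of more than 85%. The plan reproduces, but this says nothing about AD recurrence.

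**Simulation for AD recurrence.** 10,000 trials per scenario, 170 versus 85. Assumptions not in the documents:

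- 40% of subjects have IGA 4.
- The severe-versus-moderate odds ratio for any recurrence is 1, 2 or 4.
- Any-recurrence rates (placebo/active) are 37.5/26.1, 37.5/20, 35/20 or 30/15%.
- Counts are Poisson or overdispersed (negative binomial, size 0.7), cut to 0, 1, 2, ≥3.

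The row-mean-score CMH with scores 0 to 3 is

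Q = [Σₕ(Sₕ − n_Tₕ·mₕ)]² / Σₕ[n_Tₕ·n_Cₕ·vₕ/(nₕ − 1)], on 1 df.

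Here Sₕ is the active-arm score total in stratum h, mₕ and vₕ are the stratum's mean score and score variance (divisor nₕ), and n_Tₕ, n_Cₕ and nₕ are the active, placebo and total numbers.

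Power (%) in selected scenarios:

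| Placebo/active, counts, severity OR | Chi-squared 2×4 | Stratified CMH, unordered | Ordered, no strata | Stratified row-mean-score CMH |
|---|---|---|---|---|
| 37.5/26.1, overdispersed, 2 | 49.0 | 50.2 | 63.4 | 64.5 |
| 37.5/26.1, overdispersed, 4 | 47.8 | 53.4 | 63.3 | 68.0 |
| 37.5/20, overdispersed, 1 | 87.4 | 87.3 | 93.9 | 93.9 |
| 35/20, Poisson, 2 | 68.9 | 69.7 | 80.9 | 81.5 |
| 30/15, overdispersed, 2 | 79.7 | 80.1 | 89.2 | 89.6 |

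**Splitting the gain.** In the first row the total is 64.5 − 49.0 = 15.5 points. Ordering alone gives 63.4 − 49.0 = 14.4, and stratification alone gives 50.2 − 49.0 = 1.2. Over all non-null scenarios:

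- ordering alone: +6.5 to +15.5 points
- stratification alone: −0.4 to +5.6 points, the top of the range needing an odds ratio of 4
- both together: +6.5 (93.9 − 87.4) to +20.2 (68.0 − 47.8) points

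**Any recurrence versus none.** Stratified CMH against plain chi-squared gains −0.4 to +3.9 points; for example, 46.6% becomes 47.5% in the first-row scenario.

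**Type I error.** With 25% in both arms, the 2×4 chi-squared test rejects in 3.6 to 4.6% of trials and the stratified row-mean-score CMH in 4.8 to 5.2%.

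**The case against.** The strongest reply is that this is a wording question on an exploratory endpoint. The SAP never says the test is unstratified; that is inferred from silence, and the protocol synopsis itself calls the primary test a stratified CMH chi-square test. The tests are valid, no decision hangs on them, and the size of any loss depends on assumed rates. All of this stands. What survives is that the section supports two readings, and that under either one the four-category table is analysed without its ordering.

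A reader might infer several stronger things that the documents do not support:

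- *That the SAP's existing stratified CMH would recover the lost power.* It is written for response rates. Applied to the 2×4 table as a general-association test, it moves power only from 49.0% to 50.2% in the first-row scenario. The ordered version appears nowhere in the SAP.
- *That the trial is not analysed as randomised.* The arms are compared as randomised; only a stratum adjustment is missing.
- *That rescue-requiring flares are tested nowhere else.* Rescue with a major impact counts as failure in the primary and key secondary estimands (SAP 7.4.2 and 7.4.3).
- *That flares are being counted several times.* Recording by site makes this possible, but it does not establish one record per site, and Protocol 10.4.1 asks for diagnoses or syndromes rather than symptoms where possible.

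**Conclusion.** The point holds as a low-severity improvement. SAP 7.4.4 is internally inconsistent about the stratum, and its test for 0, 1, 2, ≥3 is less sensitive than a readily available alternative by roughly 6 to 20 power points. That range rests on assumed recurrence rates, count dispersion, severity mix and severity effect, none of which the documents supply. The direction, and the dominance of ordering over stratification, held in every non-null scenario tried. For any recurrence versus none, the choice hardly matters. Error control, the sample size and the primary and key secondary conclusions are untouched. Multiple counting by site is a question to confirm, not a demonstrated error.

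**What to change.** In SAP 7.4.4, specify the row-mean-score CMH stratified by baseline IGA (3 or 4) for the 0, 1, 2, ≥3 table. For any recurrence, specify the stratified CMH already defined for response rates. State the scores in advance, because they impose a chosen spacing on the categories and ≥3 is open-ended.

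Timing limits what can be changed. Protocol 6.3.2 and 12.5 plan to unblind Stage 1 at the primary analysis, and the current SAP refers to a data review meeting in October 2023. If Stage 1 is already unblinded, keep the planned chi-squared test and report the ordered test beside it, labelled as a sensitivity analysis.

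Separately, confirm that concurrent AD-recurrence records in one subject count as one episode, for both episode counts and days. If they do not, a rule for merging overlapping dates is needed.

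The cost is a few lines of SAP text and one programming option for the test. A merging rule, if needed, is a new derivation that affects how the endpoint is counted, so it should be documented as such.

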6.2.4. Follow-up Period (D393/W56, D421/W60)

After W52, subjects will not receive any study drug SC treatment, but return to the study site within the next 8 weeks to receive a follow-up visit and other study procedures.

At the follow-up visit, the subject's information to be collected or the assessment/procedure to be performed is as follows:

- Weight: Measured at W56 and W60;
- Physical examination: Performed at W60;
- VS: Monitored at W56 and W60;
- 12-lead ECG: Performed at W60;
- Eye examination: Performed at W56 and W60;
- Safety laboratory tests: Performed at W60;
- Urine pregnancy test: Only for FCBP, performed at W56 and W60;
- PK blood sample collection: Performed at W60;
- PD/ADA blood sample collection: Performed at W60;
- Investigator's efficacy assessments: Performed at W56 and W60;
- Patient reported outcomes: Performed at W56 and W60;
- PP-NRS score: The PP-NRS score of the maximum pruritus intensity in the past 24 hours is recorded every day;
- Use of mild emollients: At least twice a day;
- Assessment of injection site reactions: The previous injection site should be assessed at W56 and W60;
- AEs;
- Concomitant medication/treatment.

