4.1.3. Other efficacy endpoints

- The proportion of subjects whose IGA score is decreased by ≥ 2 points from baseline at W16;
- The proportion of subjects achieving EASI-100 at W16;
- The number of AD recurrences and number of days from baseline to W16;
- Change in efficacy parameters (e.g., IGA, EASI, BSA, SCORAD, POEM and DLQI) from

baseline to W16;

- Change in weekly average PP-NRS from baseline at W16;
- The proportion of subjects whose IGA score is 0-1 and decreased by ≥ 2 points from baseline at W52;
- Change and percentage change in the EASI score from baseline at each visit time point from the start of Stage 2 maintenance treatment to the end of study (W60);
- The proportion of subjects achieving EASI-50 at W52;
- The proportion of subjects achieving EASI-75 at W52;
- The proportion of subjects achieving EASI-90 at W52;
- The proportion of subjects achieving EASI-100 at W52;
- Change and percentage change in the weekly average PP-NRS from baseline at each visit time point from the start of Stage 2 maintenance treatment to the end of study (W60);
- Change and percentage change in POEM from baseline at each visit time point from the start of Stage 2 maintenance treatment to the end of study (W60);
- The proportion of subjects whose IGA score is decreased by ≥ 2 points from baseline at W52;
- Change and percentage change in the percentage of BSA of AD involvement from baseline at each visit time point from the start of Stage 2 maintenance treatment to the end of study (W60);
- Change and percentage change in SCORAD from baseline at each visit time point from the start of Stage 2 maintenance treatment to the end of study (W60);
- The proportion of subjects whose weekly average PP-NRS is decreased by ≥ 3 points from baseline at W52;
- The proportion of subjects whose weekly average PP-NRS is decreased by ≥ 4 points from baseline at W52;
- Change and percentage change in DLQI from baseline at each visit time point from the start of Stage 2 maintenance treatment to the end of study (W60);
- The number of subjects with AD recurrence from baseline to W8;
- The number of subjects with AD recurrence from W8 to W16;
- The number of subjects with AD recurrence from W16 to W52;
- The number of AD recurrences and number of days from W16 to W52;
- The proportion of subjects who maintain EASI-75 response at W52 to the subjects who achieve EASI-75 at W16;

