- The proportion of subjects whose IGA score remains 0-1 at W52 to the subjects whose IGA score is 0-1 at W16;
- The proportion of subjects who achieve EASI-75 at each visit time point of Stage 2 maintenance treatment to the subjects who achieve EASI-50 but not EASI-75 at W16;
- The proportion of subjects achieving EASI-50 at each of the other visit time points from the start of Stage 2 maintenance treatment to the end of study (W60);
- The proportion of subjects achieving EASI-75 at each of the other visit time points from the start of Stage 2 maintenance treatment to the end of study (W60);
- The proportion of subjects achieving EASI-90 at each of the other visit time points from the start of Stage 2 maintenance treatment to the end of study (W60);
- The proportion of subjects achieving EASI-100 at each of the other visit time points from the start of Stage 2 maintenance treatment to the end of study (W60);
- The proportion of subjects whose IGA score is 0-1 and decreased by ≥ 2 points from baseline at each of the other visit time points from the start of Stage 2 maintenance treatment to the end of study (W60);
- The proportion of subjects whose weekly average PP-NRS is decreased by ≥ 4 points from baseline at each of the other visit time points from the start of Stage 2 maintenance treatment to the end of study (W60);
- The proportion of subjects whose weekly average PP-NRS is decreased by ≥ 3 points from baseline at each of the other visit time points from the start of Stage 2 maintenance treatment to the end of study (W60);

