4.3. PK/PD Endpoints

PK endpoints: To analyze the blood concentration of CBP-201, and calculate the PK characteristics at steady-state trough concentrations of individuals and each group of subjects at each treatment time point.

PD endpoints: Change in serum IL-4, IL-13, IgE, TARC levels and peripheral blood eosinophil count from baseline.

5. Statistical Hypothesis

The primary efficacy endpoint of the study is the proportion of subjects whose IGA score is 0-1 and decreased by ≥ 2 points from baseline at W16. The following null and alternative hypotheses will be evaluated by statistical tests based on the efficacy endpoint. A two-sided significance level of 5% ($\alpha = 0.05$) will be adopted. If p value is ≤ 0.05 , the null hypothesis will be rejected and it is considered that there is a statistically significant difference in IGA parameter between the CBP-201 300 mg Q2W group and the placebo group.

Null hypothesis (H0): Efficacy in the CBP-201 300 mg Q2W group = efficacy in the placebo group

Alternative hypothesis (H1): Efficacy in the CBP-201 300 mg Q2W group \neq efficacy in the placebo group

6. Analysis Datasets

The primary analysis of the study will be performed based on the data of Stage 1, that is, placebo-controlled stage. The data of primary analysis will include all Stage 1 data from the 255 subjects who are enrolled in accordance with V2.1 and its earlier versions of the protocol. After the 255 subjects enrolled based on the V2.1 and its earlier versions of the protocol complete the treatment, related evaluations and follow-up of Stage 1 (W16 pre-dose visit), the primary analysis will be performed based on the data of the 255 subjects.

The analyses for Stage 2 will still be based on the data from 255 subjects who are enrolled in accordance with V2.1 and its earlier versions of the protocol. The data analyzed for Stage 2 will include all data from the 255 subjects who are enrolled in accordance with V2.1 and its earlier versions of the protocol that are collected from the start of Stage 2 to the end of study. After all subjects who enter Stage 2 (including the 75 subjects newly enrolled) have completed treatment, evaluation and follow-up, the analyses for Stage 2 will be performed based on the data from 255 subjects who are enrolled in accordance with V2.1 and its earlier versions of the protocol.

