RS2 will include all subjects who have been randomized to Group C or D and all subjects assigned to Group E.

RS2_R: RS2_R will include all subjects who have been randomized to Group C or D.

RS2_NR: RS2_NR will include all subjects who have been assigned to Group E.

Full analysis set 2 (FAS2)

FAS2 will include all subjects who have been randomized to Group C or D and all subjects who have been assigned to Group E and received at least one dose of the study drug in Stage 2. Subjects are analyzed within FAS2 according to treatment assigned.

FAS2_R: FAS2_R will include all subjects who have been randomized to Group C or D and received at least one dose of the study drug for Stage 2.

FAS2_NR: FAS2_NR will include all subjects who have been assigned to Group E and received at least one dose of the study drug for Stage 2.

Safety set 2 (SS2)

SS2 will include all subjects in RS2 who have received at least one dose of the study drug for Stage 2. Subjects are analyzed within SS2 according to the treatment they actually received.

Safety set 3 (SS3)

SS3 will include all subjects in SS1 and SS2 who have received at least one dose of the study drug.

PK set 2 (PKS2)

PKS2 will include all subjects who have received at least one dose of CBP-201 active drug for Stage 2 and have at least 1 collected and analyzable PK sample for Stage 2.

For the supplementary analysis based on all subjects (including the 75 subjects newly enrolled), the definitions of analysis sets are the same as above.

Table 4: Analysis Population, Treatment Group and Analysis Stage

Analysis Populations	Treatment Groups	Analysis Stage
RS1/ FAS1/ PPS1/ SS1	1) Placebo 2) CBP-201 300 mg Q2W	Stage 1 treatment period.
RS2_R/ FAS2_R	1) Placebo/CBP-201 300 mg Q2W 2) Placebo/CBP-201 300 mg Q4W 3) CBP-201 300 mg Q2W/CBP-201 300 mg Q2W 4) CBP-201 300 mg Q2W/CBP-201 300 mg Q4W 5) Q2W Total 6) Q4W Total 7) Total	From the completion of Stage 2 randomization to the end of study for subjects who have completed Stage 1 and been randomized to Group C or D.
RS2_NR/ FAS2_NR	1) Placebo/CBP-201 300 mg Q2W 2) CBP-201 300 mg Q2W/CBP-201 300 mg Q2W 3) Open-Label Q2W Total	From the start of Stage 2 to the end of study for subjects who have completed Stage 1 and been assigned to Group E.
SS2	1) CBP-201 300 mg Q2W (Group C) 2) CBP-201 300 mg Q4W (Group D)	From the first dose for Stage 2 to the end of Stage 2.

	3) CBP-201 300 mg Q2W (Group E) 4) Total	

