- Premature discontinuation of treatment/EOT due to AEs
- Use of prohibited drugs/treatments specified in the protocol as a rescue treatment for AD due to poor response, which has a major impact on the assessment of the efficacy endpoints, including:

The following prohibited drugs/treatments are used during Stage 2 (W16 to W52):

- Dupilumab or any anti-IL-4R α or IL-13 antibodies;
- Topical PDE-4 inhibitors or JAK inhibitors;
- Systemic treatment with corticosteroids or other immunosuppressive and/or immunomodulatory agents, such as cyclosporine, mycophenolate mofetil, azathioprine, methotrexate, or oral JAK inhibitors;
- Cell depletion agents (e.g., rituximab) or other biological agents;
- Other investigational drugs (non CBP-201) or treatments.

Or the following prohibited drugs/treatments are used for a cumulative period of more than 7 days during Stage 2 (W16 to W52):

- Initiation of SIT, or dose up-regulation;
- TCS or TCI (topical drugs can be used for AD lesion areas only);
- Phototherapy (NBUVB, UVB, UVA1, PUVA), sunbed or any other LED therapies;
- Bleaching baths more than 2 times a week;
- Any drug for the treatment of AD (If topical drugs, only those used for AD lesion areas will be counted) that may interfere with the evaluation of efficacy results or affect the evaluation of AD severity.

Analysis method 2: The analysis will be performed using the actual observed values. If the actual observed value is missing, it will be imputed by MI.

During MI in Stage 2, M data sets will be generated by regression method (M is set as 1000 during Stage 2 analysis).

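### Stage 2 Analysis method 1 counts rescue only up to W52 but reports response and change to W60, so its W56 and W60 estimates are neither consistently composite nor consistently as observed.

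*SAP*

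**What the plan says.** SAP 7.4.5 gives two Stage 2 efficacy analyses. Under method 1, "Categorical efficacy endpoints after the occurrence of events will be regarded as no response for subjects who have the following conditions"; continuous endpoints after such an event are replaced by WOCF, with the words 'in Stage 2' attached, and other missing data are multiply imputed. The conditions are a change of group, stopping treatment because of an adverse event, and major rescue for poor response.

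Rescue is defined by two dated lists:
- First list (systemic agents, biologics, topical PDE-4 or JAK inhibitors and others): "The following prohibited drugs/treatments are used during Stage 2 (W16 to W52").
- Second list (topical steroids or calcineurin inhibitors, phototherapy and others): "Or the following prohibited drugs/treatments are used for a cumulative period of more than 7 days during Stage 2 (W16 to W52").

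Method 2 uses observed values and imputes only what is missing.

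The reporting period is longer. SAP 6 takes the Stage 2 data as those "collected from the start of Stage 2 to the end of study". Table 4 gives the period for the randomized Stage 2 sets as "From the completion of Stage 2 randomization to the end of study". SAP 4.1.3 defines change at each "visit time point from the start of Stage 2 maintenance treatment to the end of study (W60") and response at the other visits "from the start of Stage 2 maintenance treatment to the end of study (W60"). Protocol 6.2.4 lists the investigator's "efficacy assessments: Performed at W56 and W60". SAP 7.8 records that the reporting period for the change endpoints was moved from W52 to W60.

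**The concern.** Method 1 is the Stage 2 analysis meant to treat major rescue as failure. If the event window stops eight weeks before the last reported visit, a subject given systemic rescue in follow-up can appear as a W60 responder in that analysis, while another given the same rescue slightly earlier appears as a non-responder. The reader could not then say what the W56 and W60 estimates measure. These are the off-drug durability figures for subjects who complete treatment, so the ambiguity falls on results that are likely to be read for persistence of effect.

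**Working it through.** The plan states no figure that depends on this rule, so there is nothing to reproduce. The check compares the event window with the reporting period and traces cases through the rule.

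**1. Coverage**
- Investigator efficacy visits in Stage 2 after W16 (Protocol 6.2.3.2, every 4 weeks from W20 to W52): (52 − 20)/4 + 1 = 9.
- Adding W56 and W60 (Protocol 6.2.4): 9 + 2 = 11, so 2 of 11 fall after the window.
- Time: W16 to W60 is 44 weeks and W52 to W60 is 8 weeks; 8/44 = 18%. In study days, 421 − 365 = 56.
- SAP 4.1.3 lines reported to W60: 6 change lines (EASI, PP-NRS, POEM, BSA, SCORAD, DLQI) and 7 response lines (EASI-50, -75, -90, -100, IGA 0-1, PP-NRS ≥4, PP-NRS ≥3), 13 in all.
- Of these 13, 5 are patient-reported (PP-NRS change, both PP-NRS response lines, POEM, DLQI) and are collected more often, so the 2-of-11 count describes the investigator assessments only.

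**2. Cases, for a subject with no earlier counted event**

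| Rescue for poor response | Counted? | Categorical W56/W60 value |
|---|---|---|
| Systemic, starting W51 | yes | non-response |
| Systemic, starting W53 | no | as observed |
| Second list, 10 days, all before W52 | yes (10 > 7) | non-response |
| Second list, 5 days before and 5 after W52 | no (only 5 fall in the window) | as observed |

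**3. Could another rule catch the uncounted cases?** Group change and discontinuation for an adverse event act on dosing, and the last dose is at W50 (Protocol 6.2.3.2). Multiple imputation replaces only missing values. Method 2 is as observed by design. Rescue after W52 is possible: Protocol 8.2.1 prohibits these treatments for the study period, and 8.2.2 lets the investigator give them as rescue with no W52 limit.

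**4. Continuous lines.** If Stage 2 ends at W52, WOCF confined to Stage 2 may not reach W56 or W60 even after a counted event. The 6 change lines are therefore undefined at those visits, which is why the cases above are limited to categorical endpoints.

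**5. Size.** Let r be the share of subjects whose first countable rescue falls after W52 and s the share of those observed as responders. The method 1 response rate at W56 or W60 is then higher by r × s than it would be with a window to W60. The documents give neither input. Under assumed values only:
- r = 2%, s = 25%: 0.5 points
- r = 5%, s = 50%: 2.5 points
- r = 20%, s = 100%: 20 points

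**The case against.** The strongest reply is that W52 is a deliberate on-treatment limit. The protocol separates Stage 2 (W16 to W52) from follow-up (W53 to W60) and gives no study drug in follow-up. The AD recurrence endpoints in SAP 4.1.3 stop at W52, and SAP 7.3.6 summarises rescue only for the treatment periods. Rescue first needed after treatment has ended is not plainly failure of that treatment, and how to count it is an estimand choice. That much stands. But the SAP does not state the choice, and the rule does not carry it out: an event counted before W52 still governs the categorical values at W56 and W60, so those visits are not as observed either.

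A second reply is textual. The sentence introducing the two lists has no date limit, and its 'including' could be read as non-exhaustive, so major systemic rescue at W53 might fall under it. The dated lists more naturally define the rule, but this is why the point rests on the most natural reading and not on settled scoring.

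A third reply is that nothing inferential depends on this. That is correct and limits the weight of the point.

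**Conclusion.** The mismatch is in the text and is worth correcting, at low weight. As most naturally read, method 1 at W56 and W60 mixes two ways of handling rescue, and for the change endpoints it does not say how far WOCF reaches. The number of subjects affected cannot be estimated from the documents.

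A reader might infer more than the documents support:
- *That the comparison of Groups C and D is biased.* Time off active drug does differ. The last active dose is W50 in Group C and W48 in Group D, which has placebo at W50; at W56 and W60 that is 6 and 10 weeks against 8 and 12. Late rescue therefore need not be balanced. But no rescue rate by group is given, so neither imbalance nor its direction is shown, and SAP 7.4.5 plans no Stage 2 inference.
- *That main results are affected.* The W16 primary analysis, type I error and the W20 to W52 results are untouched.
- *That late rescue goes unrecorded.* AD recurrence is recorded as an adverse event (Protocol 8.2.2), Stage 2 treatment-emergent events run to the end of follow-up (SAP 4.2.2), and recurrence-related events are tabulated (SAP 7.5.2). What is missing is the link to the response estimate.

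**What to change.** In SAP 7.4.5, Analysis method 1, for endpoints reported at W56 and W60:
- run the event window for both drug lists to W60, cumulating second-list days from W16;
- replace the WOCF wording that refers to Stage 2 with a statement that WOCF applies through W60.

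Leave the W20 to W52 results unchanged and keep method 2 as the as-observed contrast. Declaring W56 and W60 as observed under method 1 would also give a consistent rule, but only if events before W52 stopped governing those visits as well, and it would largely repeat method 2.

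The cost is SAP wording and a small derivation. Concomitant medication is already collected in follow-up (Protocol 6.2.4), so no new data are needed. W56 and W60 response rates may be lower, by an amount the documents do not allow one to estimate. The change concerns analysis only and alters no treatment or rescue rule.
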